### 6.6.3. Study Treatment Exposure

Study treatment exposure will be listed.

PFIZER CONFIDENTIAL DMB02-GSOP-RF02 8.0 Statistical Analysis Plan Template TMF Doc ID: 98.03 Page 12 of 16

### 6.6.4. Concomitant Medications and Nondrug Treatments

All prior and concomitant medication(s) as well as non-drug treatment(s) will be reported in the listings.

### 7. INTERIM ANALYSES

*No formal interim analysis will be conducted for this study.* As this is an open-label study, the sponsor may conduct unblinded reviews of the data during the course of the study for the purpose of safety assessment, facilitating PK/PD modeling, and/or supporting clinical development.

Final analysis will follow the official database release. As this will be an open-label study, there is no formal unblinding of the randomization code.

### Appendix 1. SAS Code for Analyses

An example of the PROC MIXED code is provided below:

### For the primary objective (G vs F):

proc mixed data=tab.pk; class trt participant; model l&var= trt/ ddfm=KR; random participant/subject=participant; lsmeans trt; estimate 'G vs F' trt -1 1 /cl alpha=0.1;

ods 'Estimates' out=est&var; ods 'Ismeans' out=Is&var; ods 'covparms' out=cov&var; ods 'tests3' out=tst&var;

run;

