### 6. ANALYSES AND SUMMARIES

#### 6.1. Primary Endpoints

Plasma AUC24hr, AUC24hr-last, AUClast, AUCinf and  $C_{max}$  of etrasimod will be summarized by treatment group and will include the set of summary statistics as specified in Table 3.

Parameter	Summary Statistics
AUC 24hr , AUC 24hr last, AUC inf , AUC last , C max	N, arithmetic mean, median, SD, %CV, minimum, maximum, geometric mean and geometric %CV

Natural log transformed AUC24hr, AUC24hr-last, AUCinf, AUClast, and Cmax will be analyzed using a mixed effect model with treatment as a fixed effect and participant as random effect. Estimates of the adjusted mean differences (Test-Reference) and corresponding 90% CIs will be obtained from the model. The adjusted mean differences and 90% CIs for the differences will be exponentiated to provide estimates of the ratio of adjusted geometric means (Test/Reference) and 90% CI for the ratios. Treatment F (etrasimod 2 mg, DCT Tasso PK micro samples taken by CRU staff and participants) will be the Reference treatment while Treatment G (etrasimod 2 mg, DCT Tasso PK micro samples taken by participants only) will be the Test treatment.

A listing of the individual participant ratios (Test/Reference) will be provided. Box and whisker plots for  $AUC_{24hr}$ ,  $AUC_{24hr-last}$ ,  $AUC_{inf}$ ,  $AUC_{last}$  and  $C_{max}$ , will be plotted by treatment and overlaid with geometric means.

Residuals from the models will be examined for normality and the presence of outliers via visual inspection of plots of residuals vs predicted values and normal probability plots of residuals but these will not be included in the CSR. If there are major deviations from normality or outliers then the effect of these on the conclusions will be investigated through alternative transformations and/or analyses excluding outliers. Justification for any alternative to the planned analysis will be given in the report of the study.

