### For the secondary objective (G or F vs A):

proc mixed data=tab.pk; class trt; model l&var= trt/ ddfm=KR; Ismeans trt; estimate 'F vs A' trt -1 1 0 /cl alpha=0.1; estimate 'G vs A' trt -1 0 1 /cl alpha=0.1;

```
ods 'Estimates' out=est&var;
ods 'Ismeans' out=Is&var;
ods 'covparms' out=cov&var;
ods 'tests3' out=tst&var;
```

run;

/\* Letter assignments for treatments (trt) within the estimate statement above are as follows Treatment A: Single oral dose of etrasimod 2 mg clinical IR tablet under fasted conditions (from C5041034, Reference for the secondary endpoint analysis)

Treatment F: Single oral dose of etrasimod 2 mg, DCT with practice sessions [DCT Tasso PK micro samples taken by CRU staff and participants] (Reference for the primary endpoint analysis, Test for the secondary endpoint analysis)

Treatment G: Single oral dose of etrasimod 2 mg, DCT without practice sessions [DCT Tasso PK micro samples taken by participants only] (Test for the primary and secondary endpoint analyses) \*/

PFIZER CONFIDENTIAL DMB02-GSOP-RF02 8.0 Statistical Analysis Plan Template TMF Doc ID: 98.03 Page 14 of 16

Abbreviation	Term
%CV	coefficient of variation
AA	alopecia areata
AD	atopic dermatitis
AE	adverse event
	analysis of variance
AUC 24hr	area under the plasma concentration-time profile from time zero to 24 hr
AUC24hr AUC24hr-last	Area under the plasma concentration-time profile from time 24 hr to the time of the
AUC24hr-last	last quantifiable concentration
AUCinf	area under the plasma concentration-time profile from time zero extrapolated to
	infinite time
AUC last	area under the plasma concentration-time profile from time zero to the time of the
/ CO Chast	last quantifiable concentration
BLQ	below the limit of quantification
BP	blood pressure
CaPS	Clinical Data Interchange Standards Consortium and Pfizer Standards
CD	Crohn's Disease
CI	confidence interval
Clast	last quantifiable concentration
Chast	maximum plasma concentration
	clinical research unit
CSR	clinical research diff
DCT	decentralized clinical trial
ECG	electrocardiogram
EoE	ů.
	eosinophilic esophagitis
HR	heart rate
IR	immediate-release
k el	terminal phase rate constant
LLQ	lower limit of quantification
mg	milligram
ms	millisecond
N/A	not applicable
NC	not calculated
ND	not done
NS	no sample
PD	pharmacodynamic(s)
PE	physical examination
PK	pharmacokinetic(s)
PR	pulse rate
PR interval	time from the beginning of the P wave to the beginning of the QRS complex

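### SAP Appendix 1: the primary and secondary example code read the same unfiltered dataset but need different treatment levels, so the line labelled G vs F could return F minus A

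*SAP*

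**What the plan says.** SAP Section 6.1 states the primary comparison in words: "Treatment F (etrasimod 2 mg, DCT Tasso PK micro samples taken by CRU staff and participants) will be the Reference treatment while Treatment G" is named as the Test. The model there has treatment as a fixed effect and participant as a random effect. SAP Section 3.1 gives the same direction. Treatment A, the venous arm of the main study, enters only in Sections 3.2.1 and 6.2.1, for the secondary comparisons.

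Appendix 1 then supplies code, introduced with "An example of the PROC MIXED code is provided below".

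- Primary block: "proc mixed data=tab.pk; class trt participant; model l&var= trt/ ddfm=KR", with the contrast "estimate 'G vs F' trt -1 1 /cl alpha=0.1".
- Secondary block: "proc mixed data=tab.pk; class trt; model l&var= trt/ ddfm=KR", with the contrasts "estimate 'F vs A' trt -1 1 0 /cl alpha=0.1; estimate 'G vs A' trt -1 0 1 /cl alpha=0.1".

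The comment under the secondary block describes Treatment A as "from C5041034, Reference for the secondary endpoint analysis". Neither block has a WHERE statement or other subsetting. The SAP does not define tab.pk or say which treatments it holds when each block is run.

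**The concern.** The two blocks make incompatible demands on one dataset name. The secondary contrasts match their labels only if treatment has three levels in the order A, F, G. The primary contrast matches its label only if treatment has two levels, F and G. Nothing in the appendix switches between these states.

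G against F is the only primary PK comparison, and it is reported for AUC24hr, AUC24hr-last, AUCinf, AUClast and Cmax. F against A is a different question: another study, and venous plasma against capillary serum, which SAP Section 2.1 itself reports as separate matrices. If the primary block were run on the three-treatment dataset, the output would be an estimable ratio with a 90% confidence interval and the wrong label, and no error message would be expected. Appendix 1 is the only place where the SAP writes out the contrast coefficients.

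**Working it through.** **Inputs from the SAP.** The dataset name in both blocks is tab.pk. The primary coefficients are (-1, 1). The secondary coefficients are (-1, 1, 0) for F vs A and (-1, 0, 1) for G vs A. The planned primary comparison is G (Test) over F (Reference).

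**Assumption about the software.** PROC MIXED fills a short coefficient list with zeros. This is its standard behaviour but is not stated in the documents.

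**The plan's own figures.** The plan gives no figure for this contrast. Its one design calculation, protocol Table 3, does reproduce. At a ratio of 100% for AUC, the half-width on the log scale is t(0.95, 14) × 0.281 × √(2/8) × √(χ²(0.80, 14)/14) = 0.2818, which gives 75.44% to 132.55%. Nothing below depends on it.

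**Step 1: the algebra.** Write a, f and g for the model means on the log scale.

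| Levels in tab.pk | Coefficients applied by the primary line | Result | Agrees with its label? |
|---|---|---|---|
| F, G | (-1, 1) | g − f | yes |
| A, F, G | (-1, 1, 0) | f − a | no; this is the vector the SAP labels F vs A |

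If tab.pk holds F and G only, the primary line is right but the secondary block has no Treatment A to compare with. If it holds A, F and G, the reverse applies.

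**Step 2: a noise-free illustration.** Take assumed geometric means of 100 for A, 90 for F and 99 for G. The true G/F is 99/90 = 1.10. The primary line on three levels returns 90/100 = 0.90, and would do so whatever the value for G.

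**Step 3: a fitted check.** A random-intercept REML model was fitted to simulated log data with those means. Assumptions: 8 participants with both F and G (between-participant SD 0.25, within-participant SD 0.10), and separate participants on A (SD 0.27). The documents do not give the number on A, so 8, 12, 16 and 24 were tried, with one simulated dataset each. Entries are ratios, with the log-scale standard error in brackets.

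| Number on A | Sample F/A | Sample G/F | `-1 1`, F and G only | `-1 1`, A included | `0 -1 1`, A included |
|---|---|---|---|---|---|
| 8 | 1.0703 | 1.1240 | 1.1240 (0.0187) | 1.0703 (0.1576) | 1.1240 (0.0187) |
| 12 | 0.9817 | 1.0372 | 1.0372 (0.0309) | 0.9817 (0.1025) | 1.0372 (0.0306) |
| 16 | 0.9649 | 1.0758 | 1.0758 (0.0206) | 0.9649 (0.1169) | 1.0758 (0.0206) |
| 24 | 0.9682 | 1.1338 | 1.1338 (0.0837) | 0.9682 (0.0867) | 1.1338 (0.0821) |

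In every run, `-1 1` with A included equals the sample F/A ratio and is identical to `-1 1 0`. Restricting to F and G, or writing `0 -1 1`, returns the sample G/F ratio. The runs show which quantity each line estimates. They do not predict the size of an error in this trial.

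**The case against.** A reader might infer that the SAP's primary analysis, as written, estimates F minus A. The documents do not support that.

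- They never say that tab.pk contains Treatment A when the primary block is run.
- The secondary block writes its trailing zero explicitly, which suggests an author who gives one coefficient per level and had two levels in mind for the primary block. On that reading `-1 1` is correct.
- The code is labelled an example and uses macro placeholders. Sections 3.1 and 6.1 state the comparison without ambiguity.

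The mistake would also probably be noticed. The lsmeans line would print three means. Section 6.1 requires geometric means by treatment and a listing of individual G/F ratios; with complete pairs, the model's G/F ratio equals the ratio of the geometric means. The mislabelled value would not normally match these, and would raise the question.

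A second tempting inference is that including A would distort the variance for G against F. The check gives no material support: with the right contrast, adding A moved the standard error by at most 0.0016 (0.0837 against 0.0821).

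These arguments reduce the weight of the point but do not remove it. Whichever treatments tab.pk holds, one of the two blocks does not work, and the restriction that would reconcile them appears nowhere in the SAP.

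**Conclusion.** The example code in Appendix 1 is internally inconsistent. If the shared tab.pk holds A, F and G, as the secondary block requires, the line labelled G vs F returns F minus A, contrary to Section 6.1. If it holds F and G only, the primary line is correct and the secondary block fails.

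The severity is minor to moderate. The governing text is right, the study tests no hypothesis, and the wrong result is conditional on how the dataset is built. What raises it above a matter of style is that the affected line produces the primary estimate. No error size can be given, because it would be the gap between the observed F/A and G/F ratios, which the documents cannot supply; the ratios shown in the check are illustrations under stated assumptions. The conclusion rests on the zero-filling of short coefficient lists and on the level order A, F, G that the secondary contrasts imply.

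**What to change.** Any one of these resolves the inconsistency:

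- add `where trt in ('F','G');` to the primary block, which makes the code match Section 6.1 directly;
- keep A in the data and write the primary contrast as `trt 0 -1 1`;
- give the two analyses separately named input datasets and state which treatments each contains.

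As optional good practice, add the `/e` option so that the coefficient vector is printed and can be checked, and use different output dataset names, since both blocks currently write to the same ones.

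The cost is a line or two of appendix code, before the primary model is run. Design, data collection and the text of Section 6.1 are unaffected.

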### For the secondary objective (G or F vs A):

proc mixed data=tab.pk; class trt; model l&var= trt/ ddfm=KR; Ismeans trt; estimate 'F vs A' trt -1 1 0 /cl alpha=0.1; estimate 'G vs A' trt -1 0 1 /cl alpha=0.1;

```
ods 'Estimates' out=est&var;
ods 'Ismeans' out=Is&var;
ods 'covparms' out=cov&var;
ods 'tests3' out=tst&var;
```

run;

/\* Letter assignments for treatments (trt) within the estimate statement above are as follows Treatment A: Single oral dose of etrasimod 2 mg clinical IR tablet under fasted conditions (from C5041034, Reference for the secondary endpoint analysis)

Treatment F: Single oral dose of etrasimod 2 mg, DCT with practice sessions [DCT Tasso PK micro samples taken by CRU staff and participants] (Reference for the primary endpoint analysis, Test for the secondary endpoint analysis)

Treatment G: Single oral dose of etrasimod 2 mg, DCT without practice sessions [DCT Tasso PK micro samples taken by participants only] (Test for the primary and secondary endpoint analyses) \*/

PFIZER CONFIDENTIAL DMB02-GSOP-RF02 8.0 Statistical Analysis Plan Template TMF Doc ID: 98.03 Page 14 of 16

Abbreviation	Term
%CV	coefficient of variation
AA	alopecia areata
AD	atopic dermatitis
AE	adverse event
	analysis of variance
AUC 24hr	area under the plasma concentration-time profile from time zero to 24 hr
AUC24hr AUC24hr-last	Area under the plasma concentration-time profile from time 24 hr to the time of the
AUC24hr-last	last quantifiable concentration
AUCinf	area under the plasma concentration-time profile from time zero extrapolated to
	infinite time
AUC last	area under the plasma concentration-time profile from time zero to the time of the
/ CO Chast	last quantifiable concentration
BLQ	below the limit of quantification
BP	blood pressure
CaPS	Clinical Data Interchange Standards Consortium and Pfizer Standards
CD	Crohn's Disease
CI	confidence interval
Clast	last quantifiable concentration
Chast	maximum plasma concentration
	clinical research unit
CSR	clinical research diff
DCT	decentralized clinical trial
ECG	electrocardiogram
EoE	ů.
	eosinophilic esophagitis
HR	heart rate
IR	immediate-release
k el	terminal phase rate constant
LLQ	lower limit of quantification
mg	milligram
ms	millisecond
N/A	not applicable
NC	not calculated
ND	not done
NS	no sample
PD	pharmacodynamic(s)
PE	physical examination
PK	pharmacokinetic(s)
PR	pulse rate
PR interval	time from the beginning of the P wave to the beginning of the QRS complex
QRS	combination of Q-, R- and S- wave on an electrocardiogram representing ventricular
	depolarization
QT	time from the start of the Q- wave to the end of T- wave, which represents time
	taken for ventricular depolarization and repolarization
QTc	corrected QT
QTcF	corrected QT (Fridericia method)
RR	time between the start of one QRS complex and the start of the next QRS complex
SAP	statistical analysis plan
SD	standard deviation
S1P	sphingosine 1-phosphate
S1P 1,4,5	S1P receptors 1, 4, and 5

# Appendix 2. List of Abbreviations

PFIZER CONFIDENTIAL DMB02-GSOP-RF02 8.0 *Statistical Analysis Plan Template* TMF Doc ID: 98.03 Page 15 of 16

Abbreviation	Term
SoA	schedule of activities
TEAE	treatment emergent adverse event
T max	time to C max
UC	ulcerative colitis

PFIZER CONFIDENTIAL DMB02-GSOP-RF02 8.0 *Statistical Analysis Plan Template* TMF Doc ID: 98.03 Page 16 of 16
